10.5.8.1.6. Relationship

The investigator is obligated to assess the relationship between the study treatment and each occurrence of each AE. The AE relationship to study treatment must be characterized as 1 of the following categories:

Not Related:	The AE does not follow a reasonable temporal sequence from administration of the drug, does not abate upon discontinuation of the drug, does not follow a known or hypothesized cause-effect relationship, and (if applicable) does not reappear when the drug is reintroduced, furthermore, there may exist a clear alternative medical
--------------	--

	explanation (e.g., underlying disease state) or association with study procedure or study conduct.
Unlikely Related:	The temporal association between the AE and the drug is such that the drug is not likely to have any reasonable association with the AE.
Probably Related:	The AE follows a reasonable temporal sequence from administration of the drug and cannot be reasonably explained by the known characteristics of the subject's clinical state, environmental or toxic factors, or other modes of therapy administered to the subject.
Related:	The AE follows a reasonable temporal sequence from administration of the drug, abates upon discontinuation of the drug, follows a known or hypothesized cause-effect relationship, and (if appropriate) reappears when the drug is reintroduced.

The investigator will use clinical judgment to determine the relationship. Alternative causes, such as underlying disease(s), concomitant therapy, and other risk factors, as well as the temporal relationship of the event to the study treatment administration should be considered and investigated. The investigator should consult the IB and the Product Information of marketed products within the drug class, when applicable. For each AE, the investigator must document in the medical notes that he/she has reviewed the AE and has provided an assessment of causality. There may be situations in which an SAE has occurred, and the investigator has minimal information to include in the initial report to the Sponsor; however, the investigator should always make an initial assessment of causality for every event before the initial transmission of the SAE to the Sponsor. The investigator may change his/her opinion of causality based on subsequent receipt of information and send an SAE follow-up report with the updated causality assessment. The causality assessment is one of the criteria used when determining regulatory reporting requirements.

10.5.8.2. Eliciting, Recording, and Reporting Adverse Events

10.5.8.2.1. Eliciting Adverse Events

Subjects will be instructed that they may report AEs at any time. An open-ended or nondirected method of questioning should be used at each study visit to elicit the reporting of AEs.

10.5.8.2.2. Recording Adverse Events

The AE reporting period for safety surveillance begins when the subject is initially included in the study (date of first signature of informed consent) and continues up to 30 days after the last study treatment administration. If an AE is not resolved or stabilized by this time, the Sponsor in consultation with the investigator will decide whether to continue to monitor the AE or closeout the event in the database if no further follow-up is necessary.

Any SAE suspected to be related to the study treatment must be reported whenever it occurs, irrespective of the time elapsed since the last administration.

Investigator and study personnel will record all AEs and SAEs whether received through an unsolicited report by a subject, elicited during subject questioning, discovered during physical

examination, laboratory testing, and/or other means by recording them on the eCRF and SAE Report Form, as appropriate. The following information should be recorded on the AE eCRF:

- Description including onset and resolution dates
- Whether it met SAE criteria
- Severity
- Relationship to study treatment or other causality
- Outcome

For SAEs, events occurring secondary to the primary event should be described on the eCRF in the narrative description field.

The following should be considered when recording SAEs:

- Death is an outcome of an event. The event that resulted in the death should be recorded and reported on the eCRF.
- For hospitalizations, surgical, or diagnostic procedures, the illness leading to the surgical or diagnostic procedure should be recorded as the SAE, not the procedure itself. The procedure should be captured in the narrative as part of the action taken in response to the illness.

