8.2. Discontinuation from the Study

Subjects may discontinue from the study at any time for any of the following reasons:

- AE
- Death
- Pregnancy (Section [10.5.9](#))
- Protocol deviation
- Physician decision
- Withdrawal by subject
- Lost to follow-up
- Study terminated by Sponsor
- Criteria met from cardiac heart rate monitoring to discontinue study treatment (Section [10.5.7.4](#))
- Other

A subject may elect to discontinue study participation at any time for any reason without prejudice to their future medical care by the physician or at the institution. Subjects who discontinue study treatment during the Double-Blind Study Period but who consent to remain in the study will continue to comply with study visits and assessments.

If a subject withdraws consent, no further evaluations should be performed, and no additional data should be collected. The Sponsor may retain and continue to use any data collected before such withdrawal of consent. The investigator should make a reasonable attempt to document the specific reason why consent was withdrawn.

An end of treatment (EoT) visit should be completed within 1 week of when study treatment has been terminated and a Safety Follow-Up Visit 4 weeks after the last dose of study treatment. Whenever possible, subjects should continue on study even when study treatment has been discontinued during the Double-Blind Treatment Period.

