9.3. Early Study Treatment Termination

Subjects who stop taking their study treatment before the end of the Double-Blind Treatment or Open-Label Extension Periods will return to the study site for an EoT Visit within 1 week of the last study treatment administration. Subjects who stop taking their study treatment before the end of the Double-Blind Treatment Period are not eligible to participate in the Open-Label Extension Period. Visit assessments are detailed in the [REDACTED]. Study site staff will work with subjects who withdraw early to obtain as much follow-up data as possible. Lymphocyte counts should be monitored until returned to approximately baseline or stable. In the Double-Blind Treatment Period, whenever possible, subjects should continue in the study even if study treatment has been discontinued. Subjects who discontinue study treatment, but who consent to remain in the study will continue to comply with study visits and assessments.

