10.5.7.3. Guidance on Monitoring Subjects for Infections

[REDACTED]

Therefore, investigators and subjects should be vigilant in monitoring for signs and symptoms of infections during the trial and after discontinuation of study treatment. Subjects should be instructed to promptly report to their treating physicians and investigator any signs and symptoms of infection (eg, fever, visualized red or swollen body parts). All infections that develop during the study will be reported as AEs on the respective eCRF pages ([Appendix 2](#)).

All infections that develop during the study will be reported as AEs on the respective eCRF pages. In the case of suspected or confirmed serious or atypical infection that is considered related to study treatment, study treatment interruption should be considered, and the Investigator should inform the medical monitor of any such cases. The elimination half-life of approximately 33 hours allows washout of etrasimod within a week.

Additional evaluations will be performed at the discretion of the Investigator and/or specialist consultants.

[REDACTED]

All radiologic images (eg, magnetic resonance imaging, computer tomography, x-rays) and diagnostic laboratory test results performed by local laboratories/facilities should be retained as source documents by study sites and made available upon request by the Sponsor for central adjudication as needed. All infections that develop during the study will be reported as AEs on the respective eCRF pages.

The Investigator should consider early treatment with specific antimicrobial therapy on the basis of clinical diagnosis or suspicion thereof (eg, antiviral treatment for herpes simplex or zoster) and may consult with infectious disease experts, as appropriate.

[REDACTED]

[REDACTED]

[REDACTED]

[REDACTED]

- [REDACTED]
- [REDACTED]
- [REDACTED]
- [REDACTED]
- [REDACTED]

[REDACTED]

[REDACTED]	[REDACTED]	[REDACTED]	[REDACTED]
[REDACTED]	[REDACTED]	[REDACTED]	[REDACTED]
[REDACTED]	[REDACTED]	[REDACTED]	[REDACTED]
[REDACTED]	[REDACTED]	[REDACTED]	[REDACTED]

[REDACTED]

- [REDACTED]

[REDACTED]

[REDACTED]
[REDACTED]
[REDACTED]
[REDACTED]

[REDACTED]

[REDACTED]

[REDACTED]

[REDACTED]

- [REDACTED]
- [REDACTED]
- [REDACTED]

- [REDACTED]

[Redacted text block]

[Redacted]
[Redacted]
[Redacted]

[Redacted text block]

[Redacted text block]

[Redacted text block]

[Redacted text block]

[REDACTED]

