- All medications that start in the OLE Period are considered as concomitant.

Prior medications/therapies for DB Treatment Period will be summarized by treatment using WHO Drug Dictionary (WHO-DD) Anatomical-Therapeutic-Chemical (ATC) classification and preferred term (PT). The highest available level of ATC among ATC 1-4 will be presented. For example, if ATC 1, ATC 2 and ATC 3 are available, the summary table and subject listing will present ATC 3. Concomitant medications/therapies will be summarized for DB Treatment Period, OLE Period and overall using ATC and PT.

C. Adverse Events

All AEs will be coded using MedDRA Version 23.0 March 2020. A treatment-emergent AE (TEAE) is defined as:

- Any reported AE that occurs after initiation of study treatment that was not present at the time of treatment start.
- All AEs that occur in the OLE Period are considered as TEAEs.

For the determination of TEAEs, the following rules regarding the partial start date will be applied and Baseline below refers to baseline in DB Treatment Period:

- If only the year was recorded, and it is before Baseline, it is a non-TEAE; if year is the same or after Baseline, it is assumed to be a TEAE.
- If the day is missing, but month and year are before Baseline, it is a non-TEAE; if the month and year are the same as Baseline, it is assumed to be a TEAE; if the month and year are after Baseline, it is a TEAE.
- If start date is after Baseline, it is a TEAE regardless.

If the relationship to treatment is missing, the event will be conservatively considered as being related to study drug. If the severity is missing, a separate

category of missing severity will be included in the summary table, and no imputation of severity will be performed.

AE profile will be provided (for DB Treatment Period, OLE Period, and overall), by treatment group and overall as follows:

- All AEs
- Non-TEAEs (for DB Treatment Period and overall)
- All TEAEs
- Serious AEs
- Non-Serious TEAEs
- TEAEs leading to study treatment discontinuation
- TEAEs leading to study treatment interruptions
- TEAEs related to study treatment. This will include TEAEs with a drug relationship of “Probably Related” and “Related”

Summaries of the incidence of TEAEs (for DB Treatment Period, OLE Period, and overall), will be displayed by treatment according to the following:

- TEAEs by SOC in alphabetical order and PT in descending order of frequency (in etrasimod 2mg, etrasimod 1mg, and then placebo)
- SAEs by SOC and PT

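### For double-blind subjects who stop treatment early but stay on study, the protocol gives two different end points for recording infections as AEs, and the TEAE definition has no end date to settle which events count

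*Protocol*

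**What the plan says.** **When AE recording ends.** Protocol 10.5.8.2.2 starts the reporting period at consent and says it "continues up to 30 days after the last study treatment administration". Its one exception is "Any SAE suspected to be related to the study treatment must be reported whenever it occurs".

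**Infections.** Protocol 10.5.7.3 states three times: "All infections that develop during the study will be reported as AEs on the respective eCRF pages". It asks investigators and subjects to be "vigilant in monitoring for signs and symptoms of infections during the trial and after discontinuation of study treatment". No cut-off relative to the last dose appears in the visible text.

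**Who is still on study.** Protocol 8.2: "Subjects who discontinue study treatment during the Double-Blind Study Period but who consent to remain in the study will continue to comply with study visits". Protocol 9.3 adds that "whenever possible, subjects should continue in the study even if study treatment has been discontinued". Protocol 9.2.4 makes Week 16 the End of Study Visit for subjects who stopped before Week 12.

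**Eliciting AEs.** Protocol 10.5.8.2.1: "An open-ended or nondirected method of questioning should be used at each study visit to elicit the reporting of AEs".

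**What is tabulated.** SAP 9.C defines a TEAE as "Any reported AE that occurs after initiation of study treatment that was not present at the time of treatment start", and Protocol 11.8.2 has essentially the same clause. Both set a start and neither sets an end.

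**The concern.** An early stopper who stays on study can pass the end of the 30-day period and still have several visits to come. A site asking about AEs at those visits, and told to record every infection, has grounds to enter a late infection. A site working from 10.5.8.2.2 has grounds not to. The visible text does not say which section takes precedence.

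The analysis does not remove the difference. With no end bound on a TEAE, an entered event goes into the double-blind TEAE tables and an unentered one does not. If entered, it counts as treatment-emergent long after the drug has gone: 10.5.7.3 gives a half-life of about 33 hours and washout within a week.

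Safety is a stated objective, and Protocol 10.2.7 excludes subjects with known active infection because the drug lowers lymphocytes. Infection counts should therefore not depend on a site's reading. Subjects may stop for AEs (8.1) or because they received systemic rescue (6.8.2). Either can differ by arm, so uneven recording could differ by arm too.

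**Working it through.** The plan states no figure on this point, so the check is day arithmetic.

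**Inputs**
- Recording period ends 30 days after the last dose (Protocol 10.5.8.2.2).
- Nominal Week 12 is Day 85 and nominal Week 16 is Day 113 (SAP 8.A, diary schedule).
- Double-blind visits are at Weeks 1, 2, 4, 6, 8, 12 and 16, within ±3 days (SAP 4.E).

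**Formula.** With last dose on Day L, the 30-day period ends on Day L + 30. The disputed time on study is max(0, 113 − (L + 30)) = max(0, 83 − L) days.

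| Last dose | 30-day period ends | Disputed days to Day 113 |
|---|---|---|
| Day 1 | Day 31 | 82 |
| Day 15 (Week 2) | Day 45 | 68 |
| Day 29 (Week 4) | Day 59 | 54 |
| Day 43 (Week 6) | Day 73 | 40 |
| Day 57 (Week 8) | Day 87 | 26 |
| Day 82 | Day 112 | 1 |
| Day 83 or later | Day 113 or later | 0 |

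Moving the Week 16 visit by ±3 days changes 54 to between 51 and 57, and 82 to between 79 and 85.

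**Example: last dose on Day 29.** Washout within a week is complete by about Day 36. The Week 6 and Week 8 visits (Days 43 and 57) fall inside the 30-day period, which ends on Day 59. The Week 12 and Week 16 visits (Days 85 and 113) fall outside it. A non-serious infection starting on Day 80 is an AE under 10.5.7.3 and outside the period under 10.5.8.2.2. Its onset is 80 − 36 = 44 days after washout, yet it meets the TEAE definition if entered.

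**Who is not affected**
- *Completers.* A last dose on Day 85 is covered to Day 115. A Week 16 visit three days late (Day 116) leaves 1 day.
- *Open-label early stoppers.* Their final visit is 4 weeks after the last dose (Protocol 9.2.6). That is L + 28, nominally two days inside the period. Staying on study off treatment is provided for only in the double-blind period.

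**Which events.** Serious infections suspected to be related are reportable at any time under both rules. That leaves non-serious infections and serious infections judged unrelated. For the latter, Protocol 10.5.8.3.1 requires reporting of all SAEs regardless of relationship but gives no end date, so the conflict is clearest for non-serious infections.

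**The case against.** The strongest reply is that the sections can be read together. Section 10.5.8.2.2 is the one that defines the reporting period. Section 10.5.7.3 is monitoring guidance and may mean only that infections are recorded as AEs. Section 10.5.8.2.1 is about how to ask, not for how long. The safety follow-up visit 4 weeks after the last dose and the pregnancy rule in 10.5.9 both fit a 30-day period. This is a fair argument for 10.5.8.2.2 as the governing rule, but the visible text never says so. Section 10.5.4 shows the protocol can use a wider formula: it covers laboratory abnormalities during study participation or within 30 days of the last dose.

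The Schedule of Assessments and parts of 10.5.7.3 are not visible, and they may say more about AE collection by visit. That limits how firmly one can say sites would diverge. It does not reconcile the two statements that are visible.

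A reader might go further and infer that the 30-day rule biases AE incidence downward in an arm with more early stoppers, and put a percentage-point size on it. The documents do not support that. They define no 16-week AE incidence regardless of treatment status, and leaving out events well after washout is a normal treatment-emergent convention. They also give no figure for subjects who stop treatment but stay on study. The 25% in the sample-size section is a drop-out rate, which is a different quantity.

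**Conclusion.** The conflict is real and in current text, but narrow. It affects double-blind subjects who stop before about Day 83 and consent to remain. For them it covers non-serious infections and serious infections judged unrelated. The disputed time is 54 days for a last dose on Day 29 and about 82 days at most, taking nominal visit days and attendance to Week 16.

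The consequence is inconsistent recording between sites, and possibly between arms, carried into the TEAE tables because the definition is open-ended. No direction of bias can be stated. How many subjects are affected is unknown, and with 40 per arm the expected numerical effect is small. The gain from a change is uniform ascertainment and a clear meaning for treatment-emergent.

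**What to change.** **Protocol 10.5.8.2.2 and 10.5.7.3.** State one recording end for double-blind subjects and cross-refer the two sections. One option is the later of 30 days after the last dose and the subject's last double-blind study visit. That agrees with the infection guidance and with asking about AEs at every visit. The sponsor should say which end it intends.

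**SAP 9.C.** Limit the main double-blind TEAE tables to onset no later than 30 days after the last double-blind dose, in all arms. Tabulate later events separately. For subjects entering the extension, end the double-blind window at the first open-label dose: a completer's 30 days runs to Day 115, just past nominal Week 16. The main tables then do not depend on how a site read the protocol, and no recorded event is lost.

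**Cost.** About one sentence in each document, a little extra AE entry for early stoppers, and one extra table. The visits and the AE questioning are already planned.

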10.5.8.2.3. Diagnosis Versus Signs or Symptoms

In general, the use of a unifying diagnosis is preferred to the listing out of individual symptoms. Grouping of symptoms into a diagnosis should only be done if each component sign and/or symptom is a medically confirmed component of a diagnosis as evidenced by standard medical textbooks. If any aspect of a sign or symptom does not fit into a classic pattern of the diagnosis, report the individual symptom as a separate AE.

10.5.8.3. Reporting Serious Adverse Events

All SAEs are subject to reporting requirements.

10.5.8.3.1. Serious Adverse Events

All SAEs, whether or not considered related to study treatment, must be reported to the Sponsor Contact **within 24 hours of becoming aware of the event.** Enter the SAE information on the eCRF, and send other available pertinent information (eg, hospital records, laboratory results) to the designated Sponsor contact:

IQVIA Pharmacovigilance

[REDACTED]

[REDACTED]

[REDACTED]

If additional follow-up information is required or becomes available for a previously reported SAE, entry of the new information on the eCRF should be completed **within 24 hours of awareness.**

Elective hospitalization and/or surgery for clearly preexisting conditions (eg, a surgery that has been scheduled prior to the subject's entry into the study) will not be reported as an SAE. All other hospitalizations, including elective hospitalizations for any condition that was not preexisting, will be reported as an SAE.

Any SAE that is ongoing when the subject completes the study or discontinues the study will be followed by the investigator until the event resolves, stabilizes or returns to baseline status.

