4. STUDY POPULATION

4.1. Inclusion Criteria – Double-Blind Treatment Period

Subjects must meet ALL of the following inclusion criteria to be eligible for enrollment into the study:

1. Men or women between ≥ 18 and ≤ 70 years of age at the time of informed consent.
2. Chronic AD, defined by Hanifin and Rajka criteria ([REDACTED]), that has been present for at least 1 year prior to the Screening Visit.
3. EASI ≥ 12 at the Screening Visit and ≥ 16 at the Baseline Visit.
4. vIGA score ≥ 3 (on the 0 to 4 vIGA scale, in which 3 = moderate and 4 = severe) involvement at the Screening and Baseline visits.
5. BSA $\geq 10\%$ of AD involvement at the Screening and Baseline visits.
6. Recent history (within 6 months prior to the Screening Visit) of inadequate response to treatment with topical medications, or when topical treatments are otherwise medically inadvisable (eg, because of important side effects or safety risks), which can be documented by medical records or by the history provided to the investigator by the subject despite optimized skin care (ie, avoidance of irritants, use of emollients).
7. Willing to apply a dose of topical emollient/moisturizer at least once daily for ≥ 1 week prior to the Baseline Visit and willing to continue daily application over the course of the study without change (ie, type, frequency, application).
8. Willing and able to comply with all clinic visits and study-related procedures and understand and complete study-related questionnaires.
9. Provide signed informed consent prior to conducting any procedures.

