10.5.8. Adverse Events

10.5.8.1. Definitions

10.5.8.1.1. Adverse Event

An AE is any untoward medical occurrence that does not necessarily have a causal relationship with this treatment. An AE can therefore be any unfavorable and unintended sign, symptom, or disease temporally associated with the use of a medicinal product, whether or not considered related to the medicinal product.

AEs can include, but are not limited to, any of the following:

- Unfavorable changes in general condition
- Subjective or objective signs/symptoms
- Concomitant disease or accidents
- Clinically relevant adverse changes in laboratory parameters over the course of the study
- Pre-existing conditions that worsen in severity, increase in frequency, or have new signs/symptoms

Information on the grading and management of laboratory abnormalities according to assessment severity is provided in [Appendix 2](#) and [Appendix 3](#), respectively.

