10.5.8.1.2. Serious Adverse Event

An AE should be classified as a serious adverse event (SAE) if it meets 1 of the following criteria:

Fatal:	The AE resulted in death.
Life-threatening:	The AE placed the subject at immediate risk of death. This classification does not apply to an AE that hypothetically might cause death if it were more severe.
Hospitalization:	The AE required or prolonged an existing inpatient hospitalization. Hospitalizations for elective medical or surgical procedures or treatments planned before the signing of informed consent in the study or routine check-ups are not SAEs by this definition.
Disabling/ incapacitating:	The AE resulted in a persistent or significant incapacity or substantial disruption of the subject's ability to conduct normal life functions.
Congenital anomaly or birth defect:	An adverse outcome in a child or fetus of a subject exposed to the study treatment before conception or during pregnancy.
Medically significant:	The AE did not meet any of the above criteria but could have jeopardized the subject and might have required medical or surgical intervention to prevent one of the outcomes listed above or involves suspected transmission via a medicinal product of an infectious agent.

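### Protocol 10.5.8.1.2 and 10.5.8.3.1 exempt different elective admissions from SAE status, so one arranged after consent for a worsened preexisting condition is serious under the first and unreported under the second

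*Protocol*

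**What the plan says.** **Definition (Protocol 10.5.8.1.2).** An AE is serious on the hospitalization criterion if "The AE required or prolonged an existing inpatient hospitalization". The carve-out is "Hospitalizations for elective medical or surgical procedures or treatments planned before the signing of informed consent in the study or routine check-ups". Its test is when the admission was planned, with routine check-ups added. It does not ask whether the condition was preexisting.

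**Reporting rule (Protocol 10.5.8.3.1).** The section opens by requiring every SAE to reach the sponsor's contact within 24 hours. It then takes "Elective hospitalization and/or surgery for clearly preexisting conditions" out of SAE reporting. The only mention of timing is an illustration introduced by an e.g., namely "a surgery that has been scheduled prior to" study entry. The next sentence is the complement: "All other hospitalizations, including elective hospitalizations for any condition that was not preexisting, will be reported as an SAE". The test is whether the condition was preexisting.

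**Related text.** Protocol 10.5.8.1.1 lists among AEs "Pre-existing conditions that worsen in severity, increase in frequency, or have new signs/symptoms". Inclusion criterion 2 in Protocol 4.1 requires chronic atopic dermatitis "that has been present for at least 1 year prior to the Screening Visit". Protocol 11.8.2 summarizes SAEs by treatment group. SAP Section 9.C tabulates serious AEs and non-serious TEAEs separately.

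**The concern.** Two sections that sites will both consult use different tests for the same decision. Atopic dermatitis is preexisting in every eligible subject, so the study disease itself falls under the wording of the reporting exemption. If it worsens on treatment and an elective admission is arranged because of that, a site applying the definition flags an SAE and reports it within 24 hours. A site applying the reporting paragraph does neither. The same holds for any comorbidity that worsens on study and leads to an elective admission or operation.

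The event is still recorded as an AE with its severity. What depends on the section consulted is its serious flag, the expedited report, and whether it is counted with the serious or the non-serious events in the by-arm summaries.

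**Working it through.** No arithmetic applies, and the plan gives no figure to reproduce. The check applies both rules to the same set of admissions. The inputs are the hospitalization criterion and carve-out in 10.5.8.1.2, the exemption and its complement in 10.5.8.3.1, and the AE definition in 10.5.8.1.1.

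| Admission | Under 10.5.8.1.2 | Under 10.5.8.3.1 | Result |
|---|---|---|---|
| Elective, planned before consent, preexisting condition | Exempt | Exempt | Agree |
| Elective, arranged after consent, preexisting condition, stable | No AE, so no SAE | Exempt | Agree |
| Elective, arranged after consent, preexisting condition that worsened and required the admission | SAE | Not reported | **Conflict** |
| Elective, arranged after consent, new condition that required the admission | SAE | Reported | Agree |
| Routine check-up, not for a preexisting condition | Exempt | Reported | **Conflict**, opposite direction |
| Emergency or unplanned, worsened atopic dermatitis | SAE | Reported | Agree |

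The third row in steps:

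1. Worsening of a preexisting condition is an AE under 10.5.8.1.1.
2. It required an inpatient stay that was not planned before consent, so the 10.5.8.1.2 carve-out does not apply and the AE is serious.
3. The admission was elective and the condition clearly preexisting, so the exemption in 10.5.8.3.1 applies as worded. That section says nothing about worsening.
4. The opening of 10.5.8.3.1 requires all SAEs to be reported. The section therefore both demands and excludes a report of the same event.

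Could grammar remove the conflict? In 10.5.8.1.2 the timing phrase might be read as qualifying only treatments. Elective procedures would then be exempt for any condition, including a new one, and 10.5.8.3.1 expressly requires admissions for new conditions to be reported. The sections disagree on either reading.

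**The case against.** **The case is narrow.** A flare severe enough to require admission is usually not elective, and an unplanned admission is an SAE under both sections. Rescue in Protocol 6.8.2 is by drug treatment and mentions no admission. This stands, and it confines the first conflict to admissions that were elective, arranged after consent and required by on-study worsening. Such admissions are not fanciful. SAP Section 6.B collects past hospitalization for complications of atopic dermatitis, and Protocol 6.8.3 foresees elective surgery in the extension after discussion with the medical monitor.

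**Other text favours the definition.** Protocol 10.5.8.2.2 says to record the illness behind a procedure, not the procedure, as the SAE. It also has the AE form state whether SAE criteria were met. Protocol 10.5.8.3 makes all SAEs reportable. This supports reading 10.5.8.1.2 as the test of seriousness, but none of it says that test overrides the exemption in 10.5.8.3.1.

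**The example shows the intent.** Pre-scheduled surgery may be all that the authors meant to exempt. But an example does not limit a rule, and the following sentence again turns on whether the condition was preexisting.

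**Stronger readings.** A reader might infer that admissions for flares in general escape SAE reporting, or that serious worsening is lost from the database. The documents do not support either: unplanned admissions are reported, and the worsening is recorded as an AE. A reader might also take the fact that every subject has the disease as a measure of how often this will happen. It shows who could be affected, not how many will be.

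**Conclusion.** The two exemptions contradict each other and the text is wrong as written. The contradiction is confined to two cases: elective admissions arranged after consent for a preexisting condition that worsened on study, and routine check-up admissions. The first risks under-reporting and the second only over-reporting.

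The size cannot be stated as a rate, because the documents give no admission frequency; it is probably low. No efficacy analysis is affected. What can change is the serious flag, the 24-hour report and the by-arm SAE count. The conclusion assumes that the e.g. illustrates and does not limit, and that no visible text gives one section precedence. It is worth correcting because the inconsistency bears on the study disease itself and the correction is small.

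**What to change.** Replace the elective-hospitalization paragraph in Protocol 10.5.8.3.1 with a cross-reference to the test in 10.5.8.1.2. State the consequence in one sentence: an admission required by on-study worsening of a preexisting condition, atopic dermatitis included, and not planned before consent is reported as an SAE. The cross-reference also settles the routine check-ups, which stay exempt.

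No further condition is needed. Limiting the exemption for pre-planned admissions to conditions that have not worsened since consent would be a new rule, found in neither section, and not a reconciliation.

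The cost is one paragraph in an amendment, which under Protocol 12.2 goes to the ethics committees before use. The downside is possibly a few more SAE reports.
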